5.6 Accountability

The Investigator will be responsible for the dispensing, inventory and accountability of study treatment, exercising accepted medical and pharmaceutical practices and ensuring that an accurate, timely record of the disposition is maintained. The study treatment supplies and inventory must be available for inspection by the designated representatives of the Sponsor upon request.

Upon receipt of the study treatment, the Investigator or designee will inspect the contents and return the completed acknowledgement of receipt. Copies of all study treatment inventory records must be retained for accountability of study products and supplies. Accountability must be documented from the time of initial receipt at the study centre to their final removal from the centre or destruction.

Written records must also be maintained to confirm the purpose and reason for any study treatment disposal, e.g. the amount contaminated, broken, or lost, and the name/signature of the personnel responsible for destruction. No study material (including used vials) may be destroyed until final study treatment accountability has been performed and written approval has been received from the Sponsor.

At the end of the study, the unused study treatment will either be destroyed locally or returned to the Sponsor for destruction after accountability has been verified.

5.7 Method of Assigning Patients to Treatment Groups

All patients consented will be assigned a screening number using the study centre's standard convention.

Patients will receive three different treatments in the study (see Section 5.1) at Visit 2 to Visit 4 in a randomised sequence. Randomisation numbers will be allocated using a three number format.

A dummy randomisation schedule will be approved by the Sponsor before the final randomisation schedule is produced.

5.8 Blinding

RPL554 and placebo will be administered double blind. It has not been possible to completely match the placebo to RPL554 as the visual appearance is different. The study personnel preparing the RPL554 and placebo, placing them into the nebuliser and supervising study treatment administration will therefore not be blinded to treatment identity. The dosing cup on each nebuliser will be obscured with tape to visually blind the study treatment. The Sponsor, Investigator (defined as Principal Investigator and all study physicians), all patients and all other research personnel (except bioanalytical personnel performing the pharmacokinetic assays) will therefore be blinded to the treatment allocation.

Individual tamper evident code break envelopes will be generated for each patient identifying the treatment allocation. A set of envelopes will be held by the Sponsor's Medical Monitor and each Investigator for use in the event of the need for emergency unblinding. In both cases, the code break envelopes must be held in a secure restricted-access location that is accessible 24 hours a day.

The blind should be broken only if specific emergency treatment would be dictated by knowing the treatment status of the patient. If the blind needs to be broken, the Investigator should open, sign and date the correct envelope, if possible having discussed it with the Sponsor's Medical monitor in advance.

Otherwise, all blinding will be maintained until all queries are resolved and the database is locked.

5.9 Prior and Concomitant Therapies and Medications

5.9.1 Prior and Concomitant Therapies

Prior therapies for CF taken in the last 3 months and all concomitant therapies for CF will be recorded in the CRF, with the medication, route of administration, dose and start and stop date(s) and time(s) clearly recorded to document all required washout periods and compliance with the inclusion and exclusion criteria. Any oral medications for CF used at screening should be continued during the study, preferably at a stable dose, as deemed appropriate by the Investigator.

Patients taking inhaled steroids may continue their medication only if the dose is stable from at least four weeks prior to screening and is expected to remain stable.

Long acting bronchodilators must be withheld for at least 48 hours prior to each study visit. Short acting bronchodilators must be withheld for at least 8 hours prior to each study visit. If this withhold is not met, the patient should be rescheduled for a repeat visit within 7 days.

Patients must be off antibiotics for an infectious exacerbation for at least 2 weeks prior to each treatment visit (Visits 2 to Visit 4). If patients become unstable between visits, their attending physician should give them appropriate therapy and reschedule the next treatment visit for 2 weeks after the last dose of antibiotics. In this instance the washout period between consecutive treatments is permitted to be longer than 14 days.

Patients may continue other prescribed non-respiratory therapies during the study that the Investigator considers to neither compromise subject safety nor affect study data. Pulmonary rehabilitation programs should not be started or completed during this period. Oxygen therapy on a regular basis is an exclusion criterion for this study.

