3 INVESTIGATIONAL PLAN

3.1 Overall Study Design and Plan Description

This is a Phase IIa, randomised, double blind, placebo controlled, double dummy, complete block three way crossover study to investigate the pharmacokinetics of nebulised RPL554 in adult patients with CF. It is planned to enrol sufficient patients to ensure that 10 complete all three treatment periods at two centres. The study comprises the five visits shown in Figure 1: screening (Visit 1), three treatment visits (Visit 2 to Visit 4) and an end of study visit (Visit 5). The procedures performed at each visit are summarised in Section 6 and the study assessments are described in Section 7.

Figure 1 Study Flow Chart

[a] May be performed as a single visit or more than one visit (for example if the patient is taking medications that require washout for the reversibility test)

[b] Patients will be randomised pre-dose at Visit 2

Patients will be screened for eligibility (Visit 1), including a reversibility test with salbutamol between 3 and 14 days before the first dose of study treatment.

Eligible patients will then attend for three separate 1 day treatment visits (Visits 2 to Visit 4) each separated by at least a 3 day washout period. Patients will be randomised pre-dose at Visit 2. Patients will receive a single nebulised dose of 1.5 mg RPL554 or 6 mg RPL554 or placebo at each visit. At each visit, patients will be resident at the study centre from the morning until at least 8 hours after dosing. Patients will be discharged after 8 hours, but return the following morning for final assessments 24 hours after dosing.

The following will be performed at each treatment visit:

- Measurements of lung function (FEV₁ and forced vital capacity [FVC]) pre-dose and up to 24 hours post-dose
- Blood sampling pre-dose and up to 24 hours post-dose for pharmacokinetic analysis
- Sputum sampling pre-dose and at 8 and 24 hours post-dose for rheology and measurement of inflammatory mediators (interleukin 8 [IL-8], tumour necrosis factor alpha [TNF- α] and myeloperoxidase [MPO])

- Exhaled breath pH measurement pre-dose and at 8 and 24 hours post-dose (at UK centre only)
- Urine pregnancy test pre-dose (female patients only)
- Vital signs and 12-lead electrocardiograms (ECG) pre-dose and up to 8 hours post-dose

An end of study visit (Visit 5) will be performed 3 to 10 days after the last dose of study treatment.

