6.2.1 Pre-Dose Assessments

- Confirm that respiratory medications were withheld as required. If not reschedule the visit for within the required window
- Questioning for adverse events
- Concomitant medication check
- Urine pregnancy test (female patients only)
- Nebuliser inhalation training
- 12-lead ECG
- Vital signs (blood pressure and pulse rate)

- Blood sample for pharmacokinetics
- Exhaled breath pH (UK centre only)
- Sputum for rheology and inflammatory mediator measurements
- Spirometry (one measurement at -15 minutes)

Eligible patients will then be randomised and receive a randomisation number.

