10.3.2 Secondary Endpoints

- Peak and AUC FEV₁ over 4, 6 and 8 hours
- Determination of onset of action
- Determination of duration of action
- Safety and tolerability:
 - Continuous monitoring of adverse events
 - Laboratory safety tests [haematology, biochemistry and urinalysis]
 - 12-lead ECG (including QTcF and heart rate), supine vital signs [blood pressure and pulse rate] over 8 hours

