6.4.6 Pharmacodynamic Analysis

6.4.6.1 Spirometry

For FEV_1 the average effect, (E_{av}), will be calculated as the Area Under the Curve (AUC) divided by the length of the time interval of interest. The AUC will be computed using the linear trapezoidal rule. Linear interpolation/extrapolation will be used to fill in a missing value (at most one missing value allowed) at end of the computational interval prior to calculation. In addition, the peak effect on FEV_1 will be computed as the maximum value (E_{max}) within 4 hours post-dosing. In analysis, E_{av} and E_{max} will be normalized using the baseline value.

Computed pharmacodynamic parameters for FEV_1 will be compared between placebo and the two doses of RPL554 using analysis of covariance (ANCOVA) models with fixed factors for treatment, period and patient, and using the baseline of the day as a covariate. FEV_1 will be analysed using multiplicative models, which means that data is logged prior to analysis and the result then transformed back to the linear scale giving treatment differences as ratios of geometric means. All three pairwise comparisons will be stated and expressed as the geometric mean ratio with 95% confidence interval and associated, 2-sided, p-value.

All spirometry data will be listed and summarized by treatment and assessment point as well as the change from baseline. Pharmacodynamic parameters will be

summarized by treatment. Graphics will include individual and mean FEV₁ and FVC curves over time (expressed as change from baseline on absolute scale) and scatter plots of computed pharmacodynamic parameters with the mean levels indicated.

Onset of effect will be defined as time to reach a 10% increase in FEV₁ counted from start/end of nebulization. Patients not reaching a response after 2 hours will be censored. Outcome will be illustrated using a Kaplan-Meier plot and, if appropriate, the median time to onset by (active) treatment group determined.

Duration of effect will be assessed by consecutively testing effect of active treatment versus placebo for increasing time points using similar models as the analysis of the pharmacodynamics parameters. If missing values exist, these will be filled in using linear interpolation/extrapolation prior to analysis.

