Appendix 2 Allowed and Disallowed Concomitant Medication

Patients taking inhaled steroids may continue their medication only if the dose is stable from at least four weeks prior to screening and is expected to remain stable.

All long acting (once or twice daily) bronchodilators will be stopped at the screening visit and are not allowed during the study. Patients should not use a long acting bronchodilator (long acting muscarinic antagonists [LAMA], long acting beta₂-agonists [LABA], or combination LABA/inhaled steroid) on the day of screening.

- Patients taking LAMAs and LABAs should be placed on short acting bronchodilators (e.g. salbutamol, ipratropium or Combivent) as per the discretion of the Investigator. These can be dosed on a regular scheduled basis and/or as needed use
- Patients taking combination products should be prescribed the inhaled steroid at the same or equivalent dose contained in the combination product to allow continuation of steroid use regularly throughout the study while stopping the LABA component

Patients currently taking terbutaline will be switched to other short acting bronchodilators (e.g. salbutamol).

Short acting bronchodilators must be withheld for at least 8 hours prior to spirometry at each study visit (Visit 1 to Visit 4). If this withhold is not met, the patient should be rescheduled for a repeat visit within 7 days.

Patients may continue other prescribed non-respiratory therapies during the study that the Investigator considers to neither compromise patient safety nor affect study data. Pulmonary rehabilitation programs should not be started or completed during this period. Oxygen therapy is an exclusion criterion for this study.

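### Bronchodilator use between discharge and the 24 h FEV1 is governed by two different rules, and a missing 24 h value would be extrapolated (minor; affects only the 24 h point of the duration-of-action analysis)

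*Protocol*

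**What the plan says.** **Withholding.** Protocol 5.9.1: "Long acting bronchodilators must be withheld for at least 48 hours prior to each study visit". Short-acting agents have an 8 h interval tied to the visit in the same way. Sections 6.2 and 6.3 refer back to this rule, and the instruction "Confirm that respiratory medications were withheld as required" stands in the pre-dose lists (6.2.1, repeated in 6.3.1).

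**The other rule.** SAP Appendix 2: "All long acting (once or twice daily) bronchodilators will be stopped at the screening visit and are not allowed during the study". Patients on long-acting agents move to short-acting ones, which may be taken on a regular schedule. For these, "Short acting bronchodilators must be withheld for at least 8 hours prior to spirometry at each study visit (Visit 1 to Visit 4".

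**Timing.** Protocol 3.1: "Patients will be discharged after 8 hours, but return the following morning for final assessments 24 hours after dosing". Spirometry is scheduled up to 8 h and then at 24 h, with nothing in between (Protocol 7.2.1).

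**Use of the reading.** "Determination of duration of action" is a secondary endpoint (Protocol 10.3.2). SAP 6.4.6.1: "Duration of effect will be assessed by consecutively testing effect of active treatment versus placebo for increasing time points". For that analysis, "If missing values exist, these will be filled in using linear interpolation/extrapolation prior to analysis". Protocol 10.4.8 leaves to the SAP only the imputation needed for average (AUC) FEV1 effects and rules out any other.

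**Existing safeguards.** CF therapies are recorded with start and stop times (Protocol 5.9.1). Rescue use at treatment visits is summarised by treatment and listed (SAP 6.4.7.6), and concomitant medication is listed (SAP 6.4.7.7). The effect of concomitant medication is reviewed before database lock (Protocol 5.9.2), when specific data may be excluded (SAP 6.2). SAP 6.6 has a sensitivity analysis for rescue medication in the FEV1 parameters.

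**The concern.** The conduct rule ends when the visit begins, but the FEV1 profile runs 24 h further. A patient who follows the Protocol can take a maintenance bronchodilator at home in the evening and have the 24 h FEV1 measured under its effect. The SAP is written as if this could not happen with long-acting agents, but sites work to the Protocol.

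The 24 h reading is the only one after 8 h, so any statement about action beyond 8 h rests on it. If it is contaminated unequally between treatments, or if the study drug adds less on top of another bronchodilator, the 24 h active/placebo ratio is distorted.

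The fallback is also weak. A 24 h value that is missing, or is set to missing at the pre-lock meeting, falls under a fill-in rule that at the last time point can only extrapolate.

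**Working it through.** The plan gives no figure for this point, so the check is clock arithmetic, a comparison of texts and an illustration.

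**1. Can permitted use reach the 24 h reading?** The time at home is 24 - 8 = 16 h.
- A long-acting dose in that time is at most 16 h old at the reading, inside the Protocol's own 48 h interval.
- A short-acting dose between 16 h and 24 h falls inside its 8 h interval.
- At the minimum 3-day spacing (72 h), the next long-acting withhold starts about 72 - 48 = 24 h after the previous dose. The only permitted time for a long-acting dose between two such visits is then before the 24 h spirometry.

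Protocol 5.4.2 restricts alcohol and xanthines both before and during visits. The bronchodilator rule covers only the time before.

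**2. Do the two documents agree?** On long-acting agents they do not: an intermittent 48 h withhold against a stop for the whole study. SAP Appendix 1 (inclusion criterion 8) itself keeps the 48 h wording, which a full stop would make redundant. SAP 6.8, on changes to planned analyses, does not mention the difference. On short-acting agents the interval is the same, but the SAP counts it from spirometry and the Protocol from the visit.

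**3. What could contamination do to the 24 h ratio?** Illustration only. Every input is assumed, including a true ratio of 1.05.
- Equal use with the same proportional gain under both treatments cancels in a ratio: 1.050.
- Extra use by a fraction d of patients on one treatment, adding a gain g: 1.05 × (1+g)^(-d) if after placebo, 1.05 × (1+g)^d if after active.
- Equal use by half the patients, with the drug keeping a fraction s of its effect on top: 1.05^(0.5 + 0.5s).

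| Scenario | 24 h ratio |
|---|---|
| d = 0.1, g = 5%, after placebo | 1.045 |
| d = 0.3, g = 10%, after placebo | 1.020 |
| d = 0.1, g = 5%, after active | 1.055 |
| d = 0.3, g = 10%, after active | 1.080 |
| half use, s = 0.75 | 1.044 |
| half use, s = 0.5 | 1.037 |

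The error can go either way, and the documents give no use rates with which to choose a row.

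**4. What does the fill-in rule do at 24 h?** Assume the line runs through the last two readings; the SAP does not say. Then (24 - 8)/(8 - 6) = 8, and

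FEV1(24) = FEV1(8) + 8 × [FEV1(8) - FEV1(6)] = 9 × FEV1(8) - 8 × FEV1(6).

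- 2.00 L then 1.98 L (a 1% fall): 9 × 1.98 - 8 × 2.00 = 1.82 L.
- 2.00 L then 1.94 L (a 3% fall): 9 × 1.94 - 8 × 2.00 = 1.46 L.

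Relative to one reading, the error SD is sqrt(81 + 64 - 144ρ), where ρ is the assumed correlation of the two errors: 12.0 at ρ = 0, 8.5 at 0.5 and 3.9 at 0.9.

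One such value among 10 patients, compared with using the 8 h value, multiplies that treatment's geometric mean by (1.82/1.98)^0.1 = 0.992 or (1.46/1.94)^0.1 = 0.972, ignoring period and baseline adjustment. Carrying the 8 h value forward would be stable, but would present an 8 h effect as a 24 h effect.

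**5. Is the fill-in rule consistent with the Protocol?** The SAP's rule for the average effect is what Protocol 10.4.8 foresees. Its rule for the duration analysis is a second imputation, which Protocol 10.4.8 excludes.

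**The case against.** The strongest case on the other side has five parts.

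- **Short-acting agents are arguably covered.** Protocol 4.3.4 treats a visit as running up to its 24 h assessments, so the SAP's 8 h withhold before spirometry can be read to include the 24 h test. This stands in part: the rule exists, but not in the document that sites follow.
- **Safeguards are real.** A reader might infer that nothing is planned for affected values. That is wrong: rescue use is tabulated by treatment and has a sensitivity analysis, and medication is reviewed before lock. What is absent is a rule for resumed maintenance use. Nor can the lack of a later medication check be inferred from Protocol Table 2, whose cell marks are lost in the available text.
- **Scheduled maintenance use is unlikely to differ by treatment.** In a blinded crossover it should be similar across periods. Protocol 1.1 reports additive bronchodilation with salbutamol or ipratropium in COPD, over 8 h. This stands. A reader might infer that the 24 h comparison is biased, or biased in a known direction; the documents support neither.
- **The extrapolation figures need a chain of events.** A value must be missing or excluded, and the line must use the 6 h and 8 h readings. This is fair: 1.46 L is an example, not a prediction. But any missing 24 h value, whatever the cause, meets the same rule.
- **Withholding long-acting agents to 24 h has a price.** From 48 h before to 24 h after dosing is about 72 h, which at 3-day spacing means continuous withdrawal in patients with FEV1 of 40% to 80% predicted. This stands: restricting the withhold to the time before the visit is a defensible choice for these agents.

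**Conclusion.** The point holds as a minor, inexpensive improvement confined to the 24 h duration-of-action comparison. Two things are established from the text. First, the Protocol does not bar maintenance bronchodilators between discharge and the 24 h FEV1, while the SAP assumes a stricter rule for long-acting agents and a differently anchored one for short-acting agents. Second, the SAP's fill-in rule extrapolates 16 h beyond the last reading and contradicts Protocol 10.4.8.

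The size of any contamination bias is unknown. The range 1.020 to 1.080 around an assumed 1.05 shows only that it could run in either direction. The eightfold multiplier is exact if the last two readings define the line.

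The conclusion assumes that the Protocol governs conduct at the sites, and that the 24 h reading enters the duration test. The SAP does not name 24 h, but it tests successive time points without an 8 h limit and plans an FEV1 table by assessment point (14.2.2.4).

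A reader might also infer that the main FEV1 results are at risk. They are not: peak FEV1 (within 4 h) and the 4, 6 and 8 h averages come from the supervised stay, and the primary pharmacokinetic endpoint does not use FEV1.

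**What to change.** 1. **Protocol 5.9.1 and SAP Appendix 2.** State in the Protocol that short-acting bronchodilators are withheld for 8 h before the 24 h spirometry, with rescue always allowed. Make both documents give one rule for long-acting agents. Withholding these until the 24 h spirometry is optional, since it lengthens time off treatment and may need wider visit spacing.
2. **SAP 6.4.6.1.** Do not extrapolate a missing or excluded 24 h FEV1; leave it out of the 24 h comparison. This also removes the conflict with Protocol 10.4.8 at that time point.
3. **SAP 6.6.** Extend the rescue sensitivity analysis to any bronchodilator use between dosing and the 24 h FEV1, and tabulate that use by treatment. Read it only beside the main test, because it selects on use after randomisation.

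The cost is a sentence or two in the Protocol and a few lines in the SAP. Times of CF therapy and rescue use are already recorded. The 24 h comparison may lose a few values, and patients on short-acting agents have one further 8 h withhold per period.

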5.9.2 Prior and Concomitant Medications

Other prior prescription or non-prescription medications (medication, dose, route of administration, treatment duration and indication) taken 3 months before the first study treatment administration must be recorded in the CRF in order to confirm compliance with the inclusion and exclusion criteria.

All concomitant medications must also be documented in the CRF. The impact of any concomitant medications will be evaluated during the pre-database lock review and the decision taken whether to exclude the patient from any analysis populations.

5.10 Rescue Medications

Standard procedures for emergency care should be followed for any individual adverse event, whenever clinically needed (decision to be taken by the Investigator). Short acting bronchodilators may be used as rescue medication. If this is inadequate to control their symptoms they should contact the Investigator. Rescue medication use during each treatment visit must be separately documented in the CRF (medication, dose, route of administration, date and time of each administration). Protocol procedures must still continue even if rescue medication has been taken.

